5.1.3 Equipment

Only hospitals that already performs bariatric surgery will be invited to participate in the study, therefore most of the equipment, infrastructure and resources will already be at site. Written informed consent must be obtained from each patient and stored in a secure place. A local register operating in accordance with the local EC/IRB must be used for data capturing. In Norway and Sweden, hospitals will be using the SOReg. If answers to the PROquestionnaires (HRQL and GerdQ) cannot be captured electronically in the register, paper version of these questionnaires will be distributed and collected, and the answers entered manually into the local register.

pH-metry will be performed before and two years after surgery in a subgroup of patients using the Bravo-capsule.¹⁶ The capsule is attached to the mucosa of the distal oesophagus during gastroscopy.

The capsule dislodges by itself after 4-6 days and does not have to be removed. The capsule transmits data wirelessly to a receiver outside the body. It causes little or no discomfort to the patient, and allows continuous pH-measurement during a period of 48-72 hrs.

	RESEARCH PROTOCOL
Version no 4.0	Clinical intervention study

Patients having reflux symptoms responding to PPI, but with non-acidic reflux (as evaluated by the Bravo capsule) will be offered pH-impedance measurements in order to characterize the reflux further.

5.1.4 Methodology

Data will be collected prior to the operation and at six weeks, one year, two years and five years after the operation. Clinical data, and answers to the PRO questionnaires will be collected and entered into the local register at these points except at six weeks where only data on complications will be entered. Data completeness at each time point will be assessed continuously at each hospital. Interim analysis will be performed every six month for 30 day complications, and every 12 months for primary endpoints.

5.1.5 Measures to minimise bias

The study is a multicentre study with participating hospitals from at least two countries (Norway and Sweden). Patients will be allocated by randomization, and patients, health care workers and investigators will be blinded. The surgeons operation note will state that "randomization was performed according to protocol" and will not contain information on whether gastropexy was performed or not. The study coordinator at each hospital will be responsible for keeping an updated list of patients participating in the study including who has received a pexy or not. This information must be stored at a safe place and in such a way that it can be made available for caregivers if deemed necessary. An updated list should be sent to SOReg-N on the first day of every month (see also 6.6.2).

All details regarding surgical technique except whether a pexy was performed or not must be registered in SOReg. To adjust for possible surgeon-related influence on outcome, a code number must be registered in SOReg for the individual main operating surgeon. A code number will be administered from SOReg-N to qualified surgeons whom will receive an envelope containing five numbers, and each participating surgeon within that hospital must draw one number after having been certified either by the study administrator or by a locally qualified surgeon. In Sweden the prefix for each number will be "S" and in Norway "N". The individual surgeon must use the same code number during the whole study period. Patients will be informed about the importance of follow-up both for clinical and investigational reasons. For PRO, one reminder will be send to non-responders.

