5.1.2 Primary and secondary endpoints

The primary endpoint is continuous use of ARM for GORD symptoms, or reoperation due to GORD within two years. This is easily measured and registered in most bariatric surgical

	RESEARCH PROTOCOL
Version no 4.0	Clinical intervention study

registries including SOReg. Daily use of ARM due to dyspepsia during the last month (as defined in SOReg) / reoperation due to GORD will be defined as "yes", otherwise "no".

Secondary endpoints are:

- a) PRO using the GerdQ and questionnaires for HRQL. GerdQ is a six item, easy to use questionnaire developed as a diagnostic tool for GORD.¹¹ It uses a four graded Likert scale (0-3), giving a total GerdQ score range of 0-18. Besides GerdQ, the questionnaires used for evaluating HRQL will be those that are already incorporated in the hospitals that will participate in the study. In Sweden this will be the SF-36, while in Norway only the initial question from SF-36 will be used together with PROSURG.¹²
- b) GORD as evaluated by endoscopy, pH-metry and impedance.

Endoscopy: Thirty patients will be submitted to a gastroscopy prior to, and two years after LSG/LSGG. A standard formula for evaluating and describing findings at gastroscopy will be used (appendix 1).

Reflux oesophagitis will be defined according to the Los Angeles classification (LA grade A-D), where grade C and D entails high-grade oesophagitis. ¹³ LA grade C and D, Barret's oesophagus and a peptic stricture will be considered confirmatory evidence of GORD.

pH-metry: GORD will be defined according to the oesophageal acid exposure time and the number of reflux episodes per 24 hrs. ¹⁴ pH-metry will only be performed in the subgroup of 30 patients before and two years after surgery using the Bravo-capsule. Patients having reflux symptoms responding to PPI but without acid reflux as evaluated by the Bravo capsule will be offered pH-impedance measurement.

c) Presence of a hiatal hernia as evaluated by endoscopy. The distance between the teeth and diaphragm, secondly the teeth and the GOJ will be measured and the difference calculated. If a part of the remaining stomach ascends into the thorax this will predispose to reflux as it is well known that a hiatal hernia (defined as ≥2 cm difference) is a predictor of reflux.¹⁵

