Each participating hospital will point out one person to coordinate the study within that hospital. This includes patient recruitment, obtaining written informed consent, local data management, correspondence with the national coordinator and with the Project Leader / institution responsible for this study. All included patients will be given a unique patient ID number. This number is the ID that is generated automatically by SOReg. All included patients in Sweden will thus have a six digits code number and all included patients in Norway will have a five digits code number. An updated list of included patients with overview of group allocation must be kept in a safe place within the hospital. A copy of this list containing the patient ID (no name or other identifiable data) shall be sent to SOReg-N on the first day of every month (see also 5.1.5 and 5.1.6 and appendix 17.6). Hospitals participating in the Bravo-arm of the study must balance the number of patients themselves so that an equal number of patients are allocated to the pexy and no-pexy group, respectively.

6.6.3 Factors that may compromise the outcome of the clinical study / interpretation of the results

This study is a randomized trial where the patients will be randomized into two groups. Potential differences between the groups like age, preoperative use of ARM and smoking will be accounted for by statistical methods.

Potential differences in performance between surgeons will be explored and adjusted for by statistical methods if found.

Missing values at two years will be accounted for by multiple imputation as necessary. Missing value at baseline will exclude the patient from the study.

Potential differences in culture and tradition between hospitals and countries for prescribing ARM, and similarly potential differences among patients demand for having ARM will be sought overcome by standardizing the information: ARM used in conjunction with the operation should be stopped at the latest by four weeks postoperatively. Patients using ARM after this period should actively be asked about this at the first follow-up (usually six weeks), and if no obvious reason exists it should be stopped. Similarly, if a patient is using ARM at the one-, two- or five year follow-up, the reason for this should be addressed.

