6.6.4 Follow-up

The time point for follow-up will be six weeks and one, two and five years after the operation. This is an established pattern for follow-up after bariatric surgery, and patients in this study will not deviate from this. Primary outcome is continuous use of ARM due to reflux symptoms at two years after surgery, or reoperation due to GORD within two years postoperatively. This should be a sufficient period of time to represent a realistic test of the performance of the study treatment, and allow any risks associated with potentially adverse effects over that period to be identified and assessed. One-year data will not be published separately. This is partly because it is generally not recommended to publish data for outcome with less than two-year follow after bariatric surgery, and partly because according to the literature there is an increase in the use of ARM after LSG also between one and two years postoperatively.

	RESEARCH PROTOCOL
Version no 4.0	Clinical intervention study

The follow-up visit at one, two and five years will include collection of the same data as for baseline, but gastroscopy and pH-metry will only be performed at the two-year follow-up. PRO-data at follow-up will be collected internet-based if possible.

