7 STATISTICAL CONSIDERATIONS

7.1 Statistical design

Patients will be allocated in a 1:1 fashion between LSG and LSGG. Participating hospitals will administer this by block randomization with 10 patients (i.e. 5 LSG, 5 LSGG) in each block. Group allocation will be determined by opening of sealed envelopes. The envelopes will be distributed to participating hospitals from SOReg-N.

All patients will be given a unique patient number, and SOReg-N will be informed regularly about group allocation.

Analysis for outcome will be performed according to ITT. All patients will thus be analysed within the allocated group. Missing data at two and five years will be handled by multiple imputation. The main analysis for outcome will be based on logistic mixed effect models with odds ratio between groups corrected for age, smoking and surgeon. A sensitivity analysis including hospitals will also be performed.

Information on group allocation will be blinded to patients and researchers.

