7.4 Expected drop out rates

Based on clinical experience we estimate a drop out rate of \approx 20% at two years. Adding this to the equation will make it necessary to randomize 858 patients. To be on the conservative side we plan to randomize 900 patients.

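### The protocol names no back-up route for the two-year ARM answer, although the PRO form already has an internet route, a paper route and a reminder that could carry it

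*Protocol*

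**What the plan says.** **Endpoint.** Section 6.6.4 defines the primary outcome as "continuous use of ARM due to reflux symptoms at two years after surgery, or reoperation due to GORD within two years postoperatively". Section 5.1.2 makes it a yes/no variable, with ARM use taken as daily use over the preceding month under the SOReg definition.

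**Where the ARM answer comes from.** Section 6.6.4: "The follow-up visit at one, two and five years will include collection of the same data as for baseline". Section 6.6.3 adds that "if a patient is using ARM at the one-, two- or five year follow-up, the reason for this should be addressed", and appendix 17.4 has staff ask about ARM at each follow-up.

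**Retrieval tools.** Three are named, each for the questionnaires only:
- internet collection (6.6.4): "PRO-data at follow-up will be collected internet-based if possible";
- paper forms where the register cannot capture the answers electronically (5.1.3);
- a reminder (5.1.5): "For PRO, one reminder will be send to non-responders".

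**Expected loss and its handling.** Section 7.4 expects about 20% drop-out at two years: "Adding this to the equation will make it necessary to randomize 858 patients", rounded up to 900. Section 7.1: "Missing data at two and five years will be handled by multiple imputation". Section 7.10 bases imputation of the two-year main outcome on baseline and one-year data.

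**General safeguards for follow-up.** Completeness is assessed continuously at each hospital (5.1.4), patients are told why follow-up matters (5.1.5), six months are allowed for late follow-ups (6.5.5), and a local representative watches over follow-up and can escalate queries (14.3).

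**The concern.** The primary endpoint rests on one short question and its reason, plus a reoperation that section 6.6.3 expects to be uncommon in the first two years. The ARM answer therefore drives it. The written means of reaching a patient who does not attend belong to the secondary, questionnaire-based endpoints.

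Consider a patient who fills in GerdQ online at two years but does not come to the visit. The protocol describes no step that obtains this patient's ARM status, though one more question on the form would have done so. The value is instead imputed from data at least a year old. Section 6.6.4 itself reports, from the literature, that ARM use after LSG continues to rise between the first and second year, so the named predictors predate part of the change being measured. The two-year GerdQ score, which is measured at the right time and concerns the same symptoms, is not named as a predictor.

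At stake is how far the primary result depends on the assumption that, given baseline and one-year data, missing patients resemble observed ones. The protocol gives no evidence on this either way.

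**Working it through.** **Inputs.** 14% (LSG) and 7% (LSGG), total 686 (7.2); alpha 5% and power 85% (7.3); 20% drop-out and 900 randomised (7.4); 1:1 allocation (7.1). Sidedness is not stated; two-sided reproduces the protocol's figure.

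**1. The protocol's own figures.** Two-sided test, pooled variance, no continuity correction:

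n per arm = [1.960·√(2·p̄·(1−p̄)) + 1.036·√(p₁(1−p₁) + p₂(1−p₂))]² / (p₁−p₂)²

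With p̄ = 0.105, the roots are √0.18795 = 0.4335 and √0.1855 = 0.4307:

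n = (0.8497 + 0.4464)² / 0.0049 = 342.8, so 343 per arm and 686 in total. This matches.

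686 / 0.80 = 857.5, so 858. This matches too.

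**2. Power at the planned size.** 900 × 0.80 = 720 observed, 360 per arm, 180 missing.

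Power = Φ[(0.07·√360 − 0.8497) / 0.4307] = Φ(1.11) = 86.7%.

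The expected loss is already paid for.

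**3. What retrieval could add.** The documents do not say how many of the 180 would answer a form, so the whole range is shown. These are complete-case figures. Imputation from one-year data recovers some information anyway, so the true gain in power may be smaller.

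| Share of 180 recovered (assumed) | Observed | Still missing | Power |
|---|---|---|---|
| 0% | 720 | 180 | 86.7% |
| 25% | 765 | 135 | 88.6% |
| 50% | 810 | 90 | 90.3% |
| 75% | 855 | 45 | 91.7% |
| 100% | 900 | 0 | 93.0% |

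**4. How much depends on the missing patients.** At the planned rates, 360 per arm give 0.14 × 360 = 50.4 and 0.07 × 360 = 25.2 events: about 76 in all, with a between-arm difference of about 25. The 180 unobserved patients are about seven times that difference.

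Two illustrations, both by assumption, with 14% versus 7% in the observed 80%:
- Missing patients at 14% in both arms: LSGG overall = 0.8 × 7% + 0.2 × 14% = 8.4%. The difference is 14.0 − 8.4 = 5.6 points instead of 7.0.
- Missing patients at 28% (LSG) and 14% (LSGG): 0.8 × 14% + 0.2 × 28% = 16.8% versus 8.4%. The difference is 8.4 points.

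The estimate could thus move either way. The documents do not indicate which case is likelier, or whether either applies.

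**The case against.** The strongest reply is that the protocol is silent on the mode of ARM collection, and silence is not a restriction. Section 5.1.2 calls the item easily registered in SOReg, section 5.1.4 says only that clinical data are collected and entered in the local register, and nothing excludes a telephone call or a record check. A reader might infer that ARM may be recorded only in person; the text does not say so.

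A reader might also infer that a patient who misses the visit has no primary endpoint. That is wrong on two counts. Reoperation for GORD within two years makes the endpoint positive by itself, whether or not the patient attends. Otherwise the value is multiply imputed and the patient stays in the ITT analysis. What is lost is the observed ARM answer.

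Nor is clinical follow-up unprotected overall. Completeness monitoring, the allowance for late follow-ups, patient information and local surveillance all apply to it. Section 6.5.3 foresees patients leaving the PRO part while clinical data continue; the reverse case is not described. The 20% is a general drop-out rate, and those who withdraw from the study would not return a form, so the recoverable share could be close to zero.

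Finally, staff ask about the reason for ARM use, and the endpoint depends on that reason. A self-completed item loses that check.

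Most of this stands and limits the point. What remains is that monitoring detects gaps and the allowance accepts late follow-ups, but neither is a stated way to get the ARM answer from someone who returns the form and does not attend.

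**Conclusion.** This is a worthwhile, inexpensive improvement to data capture. It is not an error in the sample size or the endpoint. The protocol names no back-up capture of the ARM answer, while a form already sent at the same time point could supply one.

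A reader might take the 20% loss to mean the trial is underpowered. It is not: 720 observed patients give 86.7% against the 85% target. The possible gain in power, from nothing up to 93.0%, rests on an assumed recovery share and a complete-case calculation, and is not the main reason to act. The main reason is that each recovered answer replaces an imputed primary outcome with an observed one, so the result leans less on missing-at-random. Whether attendance is in fact related to outcome, and in which direction, cannot be judged from the protocol.

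**What to change.** - Add to the two-year PRO form the SOReg ARM item with its reason, and an item on reoperation for reflux (yes/no, date), under the same reminder and the same internet or paper route. Word the reason as it is recorded at the visit; section 5.1.2 names dyspepsia and section 6.6.4 reflux symptoms, so settle one wording first.
- Use the self-completed answer only when the visit value is missing, and flag its source.
- Add a sensitivity analysis that uses visit-recorded values only.
- In section 7.10, add two-year GerdQ to the predictors for imputing the two-year main outcome.

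**Cost.** A few more items on a form already sent. They must be fitted to the different Norwegian and Swedish questionnaire sets, and paper answers need manual entry. The primary endpoint would contain some mix of self-completed and visit-recorded answers, including the stated reason for ARM use. The source flag and the visit-only analysis make that mix visible but do not remove it. Sample size, endpoint definition and patient care are unchanged.

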5.1.6 Including more subjects to compensate for drop-outs

If the recruitment of patients are lower than expected in Norway and Sweden, hospitals in other countries (primarily Netherland) will be invited to participate.

In order to reduce drop-outs, patients will be randomized in the operating room after being anesthetized and after the surgeon has decided to proceed with a LSG, but before surgery starts. Randomization will be performed by the use of sealed envelopes containing information on group allocation. Any patient who has signed for participation but are withdrawn before randomization will be replaced by one new subject. A list of patient(s) who withdraw after inclusion must be kept at the participating hospital and the reason for withdrawal must be stated. This list should be presented to SOReg-N on the first day of every month (see also 6.6.2).

Patients who withdraw or are withdrawn from the study after randomization cannot be replaced.

	RESEARCH PROTOCOL
Version no 4.0	Clinical intervention study

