5.2.3 Concomitant therapy

Crural repair for all patients with a Hill grade IV, and for Hill grade III if judged necessary by the operating surgeon and in accordance with the first international consensus conference on reflux and LSG.¹⁷ The repair should be performed to such an extent that the diaphragmatic crura comes close to the oesophageal wall. Crural repair is shown in the illustrating video.

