6.3 Possible interactions with concomitant treatments

A crural repair is recommended in conjunction with LSG if the hiatus is enlarged.¹⁷ Although this is recommended by experts through consensus statements, it is per as today not always performed. In this study it will be standard to perform crural repair if indicated (see 5.2.3), independent of what group the patients is allocated to. A crural repair by itself might influence GORD, but since it will be performed on the same indications in both groups, the specific influence of gastropexy can be studied independently of whether crural repair have been done or not.

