17 APPENDICES

17.1 Surgical technique

Laparoscopic sleeve gastrectomy with gastropexy (supplementary to the video).

The greater curvature has been mobilized from the pylorus to the left crus. The hiatus is briefly explored and in this patient the hiatal opening does not seem enlarged. If enlarged¹, a crural

	RESEARCH PROTOCOL
Version no 4.0	Clinical intervention study

repair should be done if possible, leaving the diaphragmatic opening about the size of the oesophagus.

A 32 french tube is passed into the stomach and down to the pylorus. Torsion of the stomach while stapling is avoided.

The resection is started 1-2 cm from the pylorus. This surgeon prefers to use a black cartridge on the antrum to avoid cracks in the serosa. The resection at this part is performed loosely along the 32 french tube.

Above the incisura angularis the stapler is closer to the 32 fr tube.

The resection continues in a straight line along the tube, and ends one cm lateral to the gastro-oesophageal junction. Whether to staple through the fat pad like here, or remove parts of the fat pad in order to better visualize the gastro-oesophageal junction can be decided by the operating surgeon.

The gastric tube is removed.

Whether the upper end of the staple line is oversewn, inverted or reinforced by other means is decided by the operating surgeon. In this case no suturing or reinforcement is used.

It is important that the gastropexy starts at the upper end of the staple line. A 2-0 non-absorbable suture like Etibond is used.

The gastro-splenic ligament is approached and sutured to the upper end of the staple line. It is important to catch a good bite of the gastro-splenic ligament, preferentially larger than shown here, in order to creat a cushion attempting to prevent the cardia from intrathoracic migration.

The second stitch is placed in a similar manner including a good bite of the gastro-splenic ligament. To avoid using a thinner and weaker part of the gastro-splenic ligament, and to avoid too much traction between the tissues, the surgeon here decides to go lateral to the resection-line on the gastrosplenic ligament.

If there is a dimple or kink in the staple line on the stomach, this can be lifted by the suture as shown here.

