On the one hand the sutures should include good bites of the fatty ligament, while on the other hand a suture must not become too tight when approximating the tissues in order to avoid a pull-through of the fat or staple line. When pulling a suture in order to approximate tissues, the angle of traction must always be greater than 90 degrees on the staple line in order to avoid a possible cutting effect.

Further down, the gastroepiploic artery or arcade becomes visible, and the surgeon outlines the gastroepiploic arcade for us. This arcade should be included in the suture line in order to increase the support for the suture, reduce the risk of a pull-through and strengthen the force of downward traction on the gastric remnant.

Performing gastropexy on the antrum of the stomach might be somewhat more difficult because of the angulation for suturing if the "French position" is used, and some of you might want to suture backhand here. Standing on the patients right side could make this part of the suturing easier. The gastropexy is continued to well below the incisura angularis. Performing gastropexy on the last 3-4 centimetres of the staple line does probably not contribute to traction on the upper part of the gastric remnant and is therefore not a part of the study. It might however be performed based on the surgeons preference since it compresses the staple line and thereby potentially could reduce bleeding.

	RESEARCH PROTOCOL
Version no 4.0	Clinical intervention study

The end result of the gastropexy should be a gastric remnant without kinks and torsion, and with a continuous traction from the gastrosplenic and gastrocolic ligament in order to keep the gastro-oesophageal junction below the diaphragm.

If possible, crural repair should be performed if a hiatal hernia, a Hill grade IV and possibly also if a Hill grade III has been found either on the preoperative gastroscopy or during the operation, in accordance with the 1st international consensus conference on sleeve and reflux. The cardia is mobilized and a full hiatal dissection is performed. The gastro-oesophageal junction is brought into the abdomen. A posterior crural repair is performed with non-absorbable material using double sutures. In this case also an anterior crural suture is used in order to approximate the crura to the empty oesophagus.

1. Enlarged = Hill grad IV, and possibly Hill grade III (decided by the operating surgeon).

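### The allocation envelope is opened before surgery starts, although the arm is not needed until the sleeve is finished, so discretionary crural-repair and staple-line decisions are avoidably exposed to knowledge of the arm

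*Protocol*

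**What the plan says.** Protocol 5.1.6 sets the time of randomization: participants "will be randomized in the operating room after being anesthetized and after the surgeon has decided to proceed with a LSG, but before surgery starts". The only reason given is to reduce drop-outs. Section 7.1 sets the mechanism: "Group allocation will be determined by opening of sealed envelopes". Neither section says who opens the envelope or when the surgeon is told.

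Several decisions in the operation are discretionary:

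- Crural repair is for all Hill grade IV patients, and "for Hill grade III if judged necessary by the operating surgeon" (5.2.3). The grade need not be known beforehand. Appendix 17.1 asks for repair "possibly also if a Hill grade III has been found either on the preoperative gastroscopy or during the operation".
- At the top of the resection, the choice to staple through the fat pad "or remove parts of the fat pad in order to better visualize the gastro-oesophageal junction can be decided by the operating surgeon" (17.1).
- "Whether the upper end of the staple line is oversewn, inverted or reinforced by other means is decided by the operating surgeon" (17.1).

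Section 6.3 admits that "A crural repair by itself might influence GORD", but sets this aside: "since it will be performed on the same indications in both groups, the specific influence of gastropexy can be studied independently". Section 5.2.2 likewise defines the comparator as the same sleeve operation, lacking only the pexy.

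**The concern.** The claim in 6.3 is safe only if a judgement-based indication is applied alike whether or not the surgeon knows that a pexy will follow. Early opening puts that at risk for no operative gain.

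The appendix itself suggests why knowledge of the arm could matter. It notes that a pexy suture can lift a kink in the staple line, and that optional suturing of the lowest few centimetres might reduce bleeding. A surgeon expecting a pexy could handle the staple line or hiatus differently from one who knows there will be none.

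If repair or staple-line handling then differs by arm, the comparison mixes gastropexy with that difference. For repair this touches the primary endpoint (acid-reducing medication or reoperation for reflux). For staple-line handling it could also touch the safety comparison, since 3.4 names leaks and bleeding as the events to watch.

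**Working it through.** **1. Order of steps (protocol 17.1, with 5.1.6, 5.2.2 and 5.2.3)**

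| Order | Step | Depends on arm? | Surgeon's discretion? |
|---|---|---|---|
| 1 | Envelope opened (5.1.6) | – | – |
| 2 | Hiatus explored; crural repair if enlarged | No | Yes, for Hill III |
| 3 | Resection along the tube | No | Yes, fat pad |
| 4 | Tube removed | No | No |
| 5 | Staple line oversewn, inverted or reinforced, or left | No | Yes |
| 6 | Gastropexy from the upper end of the staple line | **Yes** | – |

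The appendix raises repair at step 2 and describes its technique again at the end. In either case the indication does not depend on the arm. Nothing in steps 2 to 5 requires the allocation.

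**2. The plan's own figures**

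Inputs: 14% v 7% (7.2), alpha 5% taken as two-sided, power 85% (7.3), 1:1 allocation (7.1). With pooled variance under the null:

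n per arm = [1.960·√(2·0.105·0.895) + 1.036·√(0.14·0.86 + 0.07·0.93)]² / 0.07² = 343 after rounding up, so 686 in total.

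686 / 0.80 = 857.5, so 858. Both stated figures reproduce. With 900 × 0.80 = 720 analysed (360 per arm), power is 86.7%. The timing of the envelope affects none of these figures.

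**3. Size of the bias (assumptions; the documents give no repair rates or repair effect)**

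Bias ≈ (share of patients open to discretion) × (between-arm gap in repair rate among them) × (absolute effect of repair on risk).

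Assume repair halves the 14% LSG risk: 0.5 × 14 = 7 points.

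- Low: 0.10 × 0.10 × 7 = 0.07 points
- Middle: 0.20 × 0.20 × 7 = 0.28 points
- High: 0.30 × 0.30 × 7 = 0.63 points

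If the extra repairs fell in the LSGG arm at its planned 7% risk, halving gives 3.5 points and these values are half as large (0.035, 0.14 and 0.315).

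**4. Effect on the error rate (also under assumptions)**

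Suppose gastropexy has no effect, risk without repair is 14%, 20% of one arm are repaired, and 360 per arm are analysed. The gap is now a share of **all** patients, a harsher scenario than in step 3. With D the spurious difference, SE = √[p₁(1−p₁)/360 + p₂(1−p₂)/360] and rejection = Φ(D/SE − 1.96) + Φ(−D/SE − 1.96).

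| Gap in repair, all patients | Risk ratio of repair 0.5: D, rejection | Risk ratio of repair 0.7: D, rejection |
|---|---|---|
| 5 points | 0.35 points, 5.2% | 0.21 points, 5.1% |
| 10 points | 0.70 points, 5.9% | 0.42 points, 5.3% |
| 20 points | 1.40 points, 8.9% | 0.84 points, 6.3% |

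Example, 10-point gap and risk ratio 0.5: p₁ = 0.14 × 0.80 + 0.07 × 0.20 = 0.126; p₂ = 0.14 × 0.70 + 0.07 × 0.30 = 0.119; D = 0.7 points.

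**5. Can the analysis repair it?**

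The main model corrects for age, smoking and surgeon (7.1). A surgeon term removes differences between surgeons, not a difference between arms within the same surgeon. Registering surgical details (5.1.5) lets an imbalance be seen. But a repair decision made after the arm is known is a post-randomization variable, so adjusting for it is no clean correction.

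**The case against.** The best defence is that the effect is small and partly guarded against. Hill IV repair leaves no choice by grade, Hill III may already be known from the preoperative gastroscopy, teams must pass a video review (6.4), and all technical details except the pexy are registered (5.1.5). This stands as mitigation. None of it prevents one surgeon from deciding differently by arm.

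Four stronger readings are tempting, and the documents do not support them:

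- **That the surgeon has certainly seen the allocation.** This is an inference. The protocol does not say who opens the envelope. It is a reasonable inference because no shielding is described.
- **That the bias is large.** A reader might assume that repair lowers risk by 10 or 15 points. Against the 14% and 7% in 7.2, a 15-point reduction exceeds the whole LSG risk, and 10 points exceeds the whole LSGG risk. Such values would need a much higher risk in Hill III patients, which the protocol does not state.
- **That later opening removes the bias entirely.** Fixed blocks of 10 per hospital (7.1), with surgeons who know the arms of patients they operated on, leave some allocations guessable late in a block.
- **That early opening costs meaningful power through changed or abandoned operations.** No frequency is given, randomization follows the decision to proceed with a sleeve, such patients stay in the ITT analysis, and 900 are planned against 858 needed.

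**Conclusion.** The point holds as an avoidable risk of performance bias, not as a demonstrated failure. The order of steps, the discretion and the assumption of equality can all be read from the protocol. The surgeon's knowledge of the arm is inferred from the absence of shielding.

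The direction is unknown: more repair in the LSGG arm would flatter gastropexy, and more in the LSG arm would dilute it. On the assumptions in step 3 the size is about 0.07 to 0.63 points, middle case 0.28, against a 7-point target. That rests on repair halving a 14% risk and on discretionary patients carrying average risk. A marked inflation of the false-positive rate (8.9%) appears only if repair doubles from 20% to 40% of all patients in one arm and also halves risk.

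The change is still worth making. The rule brings no operative benefit, and its stated aim of limiting drop-outs is served at least as well by opening later.

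**What to change.** Amend 5.1.6 so that the envelope is opened only when hiatal assessment, any crural repair, resection, tube removal and any staple-line reinforcement are complete, immediately before the point where gastropexy would start. Require the Hill grade and the crural-repair decision to be recorded before opening. State who opens the envelope. No surgical indication, sample size or alpha changes.

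The cost is a brief pause during the operation and a protocol amendment, which needs steering committee agreement and ethics approval (section 9).

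The protocol is at version 4.0 with inclusion planned for 2023–2024 (8.4), so the change may fall within recruitment and leave two procedures in one trial. If recruitment has begun, note the date of the change and report crural repair and staple-line handling by arm, before and after it.
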